Participants will be assessed during the week prior to starting the intervention (pre-intervention), the week following completion of the intervention (postintervention), and three months after completing the intervention (follow-up) (Figure 1). At the preintervention visit participants will be notified as to whether they were randomized to the tango, treadmill or stretching group. Randomization sequences will be generated a priori by an independent statistician. Prior to commencing exercise all participants will undergo a physical examination and will be required to complete an on medication screening graded exercise test per previously established protocols [44-46] in order to determine whether or not they can exercise safely. All groups will receive 12 weeks of exercise, meeting 3 times per week for one hour each session. The exercise groups will thus participate in 180 minutes of exercise per week, meeting the CDC guidelines for physical activity[17]. All groups will exercise in community-based group settings to ensure that participants have similar experiences with respect to social interactions associated with participating in a group exercise class. Participants will be assigned to groups using a process of stratified blocked randomization. Self-selected forward gait velocity measured at baseline will be used to stratify participants into three categories: <1.1 m/s, 1.1-1.3 m/s, and >1.3 m/s. These strata have been chosen based upon our preliminary data from 60 individuals tested OFF medication. The average velocity for this group was 1.2 ± 0.1 m/s (mean \pm SD). Thus the middle stratum includes individuals within one SD of the mean and the upper and lower strata include individuals more than one SD above or below the mean, respectively. Each stratum will be randomized to the 3 groups using a block size of 10 to ensure that there is no temporal bias and guarantee that the number of participants at each level of walking performance who enter each study arm is the same.

2.d Risks and Benefits

There are no identifiable legal, social, or psychological risks associated with participation in the proposed studies. The identifiable risks are minimal and we are aware of no alternative procedures that can provide the same information.

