Movement Disorder Society Unified Parkinson Disease Rating Scale (MDS-UPDRS)
Five times sit to stand (5xSTS) - 6 minute walk (6MWT) - 9 Hole Peg Test (9HPT)
PDQ-39
Forward preferred speed, forward fast, backward, tandem and dual task walking on a GAITRite computerized walkway system.
Spatiotemporal gait assessment will be completed simultaneously with the GaitRITE assessment.

Exercise training begins:

Each Participant will be assigned to a group (treadmill training, tango dance training or stretching) using a process of stratified blocked randomization and notified of their group assignment following their initial visit. This is necessary as walking speed must first be assessed prior to group assignment.

Within one week of the initial visit, the training sessions will begin. All groups will receive 12 weeks of exercise, meeting 3 times per week for one hour each session. The exercise groups will thus participate in 180 minutes of exercise per week, meeting the CDC guidelines for physical activity. All groups will exercise in community-based group

settings to ensure that participants have similar experiences with respect to social interactions associated with participating in a group exercise class

The individual groups will complete 1 hour of training following the protocol listed below:

Tango Training: Tango classes will be modeled on those of our previous studies, and will include a brief warm up and a cool down, with 45 minutes of the hour devoted to tango specifically as described previously in our lab. Participants will dance both leading and following roles and will change partners frequently in order to ensure that everyone spends time moving forward and backward and gets experience dancing with many different partners. Partners will be individuals without PD and will include spouses and caregivers of those with PD as well as healthy volunteers.

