Using PASS software (NCSS, LLC, Kaysville, UT), we have powered each aim based upon preliminary data. Our primary variable of interest in Aim 1 is gait velocity. Average forward gait velocity +/- SD was 1.2 +/- 0.1 m/s and average backward gait velocity was 0.6 +/- 0.1 in a sample of 60 individuals with PD (H&Y = 2.4 +/- 0.2) tested OFF medication in our laboratory over the past year for a different study. The study has been powered to be able to detect differences of 1 SD, or 0.1 m/s, which is equivalent to an effect size of 0.4. Changes of 0.1m/s or more in gait velocity have been reported previously following both tango [22-24] and treadmill training [8, 29, 61, 62]. With an effect size of 0.4, 27 participants per group will provide 89% power to detect differences between or within groups using two-tailed tests at a significance level of 0.05. Based upon additional preliminary data from our lab, we have determined that this sample size is also more than sufficient to adequately power our secondary variables in Aim 1 (MDS-UPDRS-III, mini-BESTest, PDQ-39).

Aims 2 and 3 have been powered based upon preliminary data from our lab and sources in the literature. For Aim 2, our preliminary data from controls before and after a single session of treadmill training indicate an effect size of 0.91 for change in beta weights using the cerebellum as an exemplar region (pre = -0.094 +/- 0.111, post = 0.418 +/- 0.116, Figure 9) during imagined forward walking. We recognize that responses in those with PD may be less pronounced than in controls and as such have used a very conservative effect size of 0.45, half the size of the effect observed in controls, for our power calculation. Our preliminary data from people with PD (n=8) imagining forward walking indicate a beta weight of -0.075 +/- 0.097, which is comparable to the value obtained from young controls at baseline. Utilizing the data from the sample with PD and an estimated effect size of 0.45, 18 subjects per group will provide 80% power to detect differences between groups and 88% power to detect within group differences.

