Significant findings of differential BOLD signal changes have been localized in PD populations during similar imagined walking MRI paradigms with a total of 12 PD participants per group [59], further supporting that our proposed sample size is likely adequate. For Aim 3, utilizing rs-fcMRI (Figures 7,8) to determine correlations between regions in the locomotor control network, we have powered the study to enable detection of differences in correlation coefficients of 0.1 (mean correlation = 1.0, SD = 0.1, p = 0.05, effect size = 0.44, per data from Wu et al. 2009 and our own preliminary data). We will have 80% power to detect between group differences and 88% power to detect within group differences with 18 subjects per group.

Based upon our previous intervention studies [23], we anticipate an attrition rate of approximately 15-20% due to dropouts or failure to complete the required minimum of 85% of classes. We also expect MRI related complications due to head motion in roughly 30% of tested individuals. This estimate is based upon our preliminary data from individuals with PD (Fig. 4, 5) where we lost 24% of scans due to head motion greater than 2mm of translation or rotation during a scan. As such, we will recruit 40 subjects per group to account for attrition and data loss due to head motion and still obtain the needed final sample sizes for each aim. For Aim 1 dropouts will be handled utilizing intent to treat analyses with the last observation carried forward. Dropouts will be excluded from analyses in Aims 2 and 3 as full imaging data are needed from two time points.

G2 Interim Monitoring and Early Stopping

The protocol will also be evaluated and the risk to benefit ratio assessed twice annually.

G3 Analysis Plan and Statistical Methods

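### A block size of 10 cannot be split evenly across three arms, so the randomisation as written cannot give the equal numbers per gait-speed stratum that the protocol says it guarantees

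*Combined protocol and SAP*

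**What the plan says.** Section 2.c (Randomization Method and Blinding) defines three strata of self-selected forward gait velocity: below 1.1, 1.1 to 1.3, and above 1.3 m/s. On allocation it states: "Each stratum will be randomized to the 3 groups using a block size of 10 to ensure that there is no temporal bias". The same sentence goes on to say that this will "guarantee that the number of participants at each level of walking performance who enter each study arm is the same".

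The other relevant statements are these:

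- Section G1 plans equal arms: "we will recruit 40 subjects per group to account for attrition and data loss due to head motion". Section E1 gives the total as 120.
- Section 2.c assigns the list to an independent party: "Randomization sequences will be generated a priori by an independent statistician".
- Sections F2 and F5 repeat only that participants are assigned "using a process of stratified blocked randomization and notified of their group assignment following their initial visit".

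No section gives an unequal ratio, the composition of a block, or a rule for the tenth place.

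**The concern.** On the usual meaning of the term, a block size is the number of consecutive assignments within which the arms occur in the planned ratio. With three equal arms it has to be a multiple of 3. A block of 10 is not, so the sentence that sets the block size contradicts the balance it claims.

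The stratification factor is the baseline value of the Aim 1 primary variable, so the balance claim concerns the covariate that matters most. In addition, the statistician who builds the list must invent a rule for the tenth place. The sequence then cannot be reproduced from the protocol, and a report that repeats the sentence would claim something impossible.

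**Working it through.** **Inputs.** Three arms, block size 10, and strata cut at 1.1 and 1.3 m/s (section 2.c); 120 participants (E1); 40 per group (G1); preliminary gait velocity 1.2 with SD 0.1 m/s (2.c, G1); effect size 0.4, 27 per group, alpha 0.05, 89% power (G1).

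**Step 1: divisibility.** 10 = 3 × 3 + 1. The most even complete block is 4:3:3. This needs no assumption and settles the main point.

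**Step 2: other readings.**

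- *Extra place rotates across arms.* Exact balance then falls only at multiples of 3 × 10 = 30 within a stratum.
- *Ten per arm.* This is a block of 3 × 10 = 30, which is not what the text says.

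The documents give no expected stratum sizes. On the cut-points, section 2.c says: "Thus the middle stratum includes individuals within one SD of the mean". If gait speed is normal (an assumption), the outer strata expect 120 × 0.1587 = 19.0 people each and the middle one 120 × 0.6826 = 81.9. An outer stratum of about 19 would usually not fill one set of 30, so neither reading delivers the guarantee.

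**Step 3: size of the imbalance.** Simulation with 6,000 runs per scheme, 120 participants, stratum sizes multinomial with the shares above, and permuted blocks within stratum. The gap is the largest arm minus the smallest, shown as median (95th percentile).

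| Scheme | Overall gap | Worst gap within a stratum |
|---|---|---|
| 10, extra place random | 4 (8) | 3 (6) |
| 10, extra place rotates, random start in each stratum | 2 (5) | 2 (3) |
| 10, extra place rotates, same start in every stratum | 3 (6) | 2 (3) |
| 30 | 4 (8) | 3 (6) |
| 9 | 2 (4) | 2 (3) |
| 6 | 2 (4) | 1 (2) |
| 6 and 9 mixed | 2 (4) | 2 (3) |

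With strata of 10/80/10% or one third each, the overall figures are the same, and the within-stratum figure for the random extra place is 3 (5 to 6). If the same arm always received the extra place, 12 complete blocks would give 48/36/36 and the simulated overall gap is 13 (16). Nothing in the documents suggests that this would be done.

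**Step 4: the guarantee.** All three strata are exactly equal in under 0.1% of runs for blocks of 10 with a random extra place, under 0.5% with a rotating one, about 2% for blocks of 9 and about 4% for blocks of 6. Final blocks are usually incomplete, so the claim is too strong for any block size.

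**Step 5: power.** G1 states: "27 participants per group will provide 89% power to detect differences between or within groups". A one-way ANOVA has noncentrality λ = f² × N. With 27 per group, λ = 0.16 × 81 = 12.96 on 2 and 78 degrees of freedom, and power is 0.895, which matches the plan. With 40 per group, before attrition, λ = 0.16 × 120 = 19.2 on 2 and 117 degrees of freedom, and power is 0.979. With unequal arms, λ = Σ nᵢ(μᵢ − μ̄)², where μ̄ is the mean weighted by nᵢ, and the result depends on which arms differ: 0.971 to 0.984 for 44/40/36, and 0.965 to 0.986 for 48/36/36.

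**Step 6: predictability of the alternatives.** Suppose an observer knows the block scheme and every earlier assignment in a stratum. The expected share that can be named with certainty is:

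- fixed 6: (1 + 1/5)/6 = 0.20
- fixed 9: (1 + 2/8 + 2/8 × 1/7)/9 = 1.286/9 = 0.14
- 10 with an unknown extra place: (0.6 + 0.6 × 2/9 + 0.6 × 2/9 × 1/8)/10 = 0.75/10 = 0.075
- 6 and 9 mixed in undisclosed order, stratum of 82: about 0.05 (simulated)

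**The case against.** The strongest objection is that this hardly matters in practice. Replacing blocks of 10 with multiples of 3 moves the median overall gap from 4 people to 2. If the extra place already rotates from a random start in each stratum, the median stays at 2, and a mix of 6 and 9 leaves the within-stratum gap unchanged at 2 (3). The independent statistician would have to settle the tenth place before producing a list, which lowers the chance of harm. All of this stands, and it keeps the point minor.

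A second objection is that two faults are being run together. The failure of divisibility is specific to this protocol. The word *guarantee* would be too strong in nearly any stratified blocked design. That is fair, and the two are corrected separately below.

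A third objection is that any multiple of 3 repairs the arithmetic, so preferring mixed sizes is a matter of judgement. The predictability figures assume an observer who knows all earlier assignments in a stratum, and the documents do not say that recruiting staff do. They say only that participants learn their own group: "At the preintervention visit participants will be notified as to whether they were randomized to the tango, treadmill or stretching group". This also stands: mixed sizes are a sensible precaution and are not needed for the correction.

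None of these objections makes 10 divisible by 3 or supplies the missing rule.

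**Conclusion.** The concern holds. Blocks of 10 cannot be balanced over three equal arms, so the procedure in section 2.c lacks the property stated in the same sentence. This is certain and rests on no model.

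The size is small. The expected imbalance is a few participants out of 120, allocation is not biased, and power before attrition stays close to 0.98 for imbalances of the likely size. The imbalance figures assume roughly normal gait speed with the preliminary mean and SD, and they depend on how the tenth place is filled, which the documents leave open. The point is a correction of specification and wording. It does not threaten the results.

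**What to change.** 1. In section 2.c, replace the block size of 10 with permuted blocks whose sizes are multiples of 3 within each stratum, preferably varied (for example 6 and 9), with the order held by the independent statistician. A single published size of 6 would also correct the balance, but it makes late assignments in a block easier to predict.
2. Replace the guarantee with a statement that the scheme keeps the numbers per arm within each stratum approximately equal.
3. If the list has already been generated, state the block sizes and composition actually used.

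The cost is negligible: one changed number and one reworded sentence, with no effect on sample size, visits or analysis. Predictability need not rise, since mixed sizes in undisclosed order give about 5% certain assignments against 7.5% for blocks of 10 with a random extra place.

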Based upon our previous intervention studies, we anticipate an attrition rate of approximately 15-20% due to dropouts or failure to complete the required minimum of 85% of classes.

2.f When and How to Withdraw Subjects

Individuals may withdraw at any time during the duration of the study

2.g Data Collection and Follow-up for Withdrawn Subjects

No follow-up will be completed for withdrawn subjects

E3 Study Drug

None

F Study Procedures

F1 Screening for Eligibility

Possible participants will be screened via a phone interview. The screening process will identify if the individual meets the inclusion criteria stated above and does not meet any of the exclusion criteria.

F2 Schedule of Measurements

Time requirements:

Screening phone call - 15-20 minutes - on medication

Pre-Intervention Evaluation - 4.5 hours - off medication

3 exercise sessions per week for 12 weeks - 1 hour each - on medication

Post Intervention Evaluation Visit - 4 hours - off medication

Follow-Up Evaluation - 12 weeks after conclusion of exercise class - 2 hours (no fMRI) - off medication

Screening phone call

Following the consent process we will complete an MRI screening form. If the individual is not excluded from completing an MRI scanning session we will continue with the screening process.

In addition, all eligible participants must be able to perform the imagined gait tasks in the MRI at or above a previously determined threshold. All participants will complete the Kinesthetic and Visual Imagery Questionnaire (KVIQ-20) (Malouin, et al, 2007) with an additional four question “imagined” gait task assessment (Pickett, Peterson & [name], 2012). The KVIQ-20 is used to assess vividness of mental imagery during motor tasks and has been previously used with PD patients (Heremans, et al, 2011). Participants with a mean KVIQ-20 + gait subsection score more than one standard deviation below the mean of an age matched healthy cohort (data recently collected in [name] lab) will be excluded from the study.

Any individual who is accepted for the study based on the above will be given a packet of questionnaires to complete at home and continue on following the procedure below. This portion will be completed with a researcher who is blinded to the individual’s group assignment. The specific questionnaires that will be included in the packet are as follows:

Epworth Sleepiness Scale

Non-Motor Symptom Questionnaire

Stages of Readiness to Exercise Questionnaire

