Effects of medication withdrawal will be monitored via patient report and if the effects are too severe, participation in the study will be terminated prior to the second day of "off medication" testing.

8.c Definitions of Adverse Events

An adverse event is any patient reported

8.d Classification of Events

We do not anticipate any adverse events; however, the following procedures will be followed to minimize the risk.

- a) Temporary Worsening of Parkinson's symptoms. A temporary worsening of Parkinson's disease symptoms may result from not taking anti-Parkinson's medication for study evaluations. Once the individual resumes taking their medication, symptoms should return to their typical levels. Effects of medication withdrawal will be monitored and if the effects are too severe, participation in the study will be terminated prior to the second day of "off medication" testing .
- b) Loss of confidentiality. Loss of confidentiality is highly unlikely. To safeguard against this, we will comply with all HIPAA regulations. Data will not be identified by subject name. All data will be coded, and code sheets will be stored in locked files.
- c) Stumbling during locomotion. Subjects will be closely attended by a physical therapist during walking. Walking will be performed in a large, open space and the therapist will be prepared to assist subjects who may stumble. It is therefore unlikely that subjects will experience falls during testing or will be injured as the result of a fall.
- d) Falling into safety harness. During testing on the treadmill, subjects will wear a modified parachute harness connected to an overhead beam that is rated to support heavy loads. A subject who falls will be supported fully by the harness and is therefore unlikely to be injured. Subjects will also be able to hold the support guides which will help them to stabilize balance during treadmill testing. In addition, the treadmill will be equipped with redundant safety features to prevent subject injury and allow immediate cessation of treadmill movement at the touch of a button.

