j) Loud noise. While inside the magnet, subjects will be able to communicate with the investigators through an intercom. To help protect the participant's hearing two levels of hearing protection will be worn by all participants. Ear plugs will be inserted into the ear and outer headphones will be placed over your ears. Also, they will be given an alarm device to press if the intercom system should be ineffective because of the loud noises. This alarm will create a definite signal to the investigators that the subject wishes to communicate or exit. If a test is in progress, the test will be stopped and investigators will either speak to the subject using the intercom or enter the room and take the patient out of the magnet.

The risks associated with these studies are minimal. Participant safety will be continuously monitored by the PI during experimental sessions and participants will be advised of how to contact the PI if they have any concerns that arise outside of these sessions.

8.e Reporting Procedures

Any adverse events will be reported to the local IRB immediately and will trigger an immediate review, like the annual review described previously, to determine what changes need to be made and whether the study should continue or conclude.

8.f Adverse Event Reporting Period

Patients will be followed for 12 weeks following their final exercise session. Adverse events will be documented throughout this period.

8.g Post-study Adverse Event

Any advent reported to the investigators following the conclusion of the study will be documented and reviewed.

G Statistical Plan

G1 Sample Size Determination and Power

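### Section 2.g ends follow-up at withdrawal while 8.f has adverse events documented for 12 weeks after the last session; followed as written, 2.g may miss later or unreported harms in withdrawn participants

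*Combined protocol and SAP*

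**What the plan says.** Section E2 2.g, whose heading covers both data collection and follow-up for people who withdraw, consists of one sentence: "No follow-up will be completed for withdrawn subjects". Section 2.f, just before it, says "Individuals may withdraw at any time during the duration of the study".

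Section F8 8.f sets the adverse event period: "Patients will be followed for 12 weeks following their final exercise session. Adverse events will be documented throughout this period". It applies to patients in general and carves out nobody.

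Section 2.e gives the expected loss: "we anticipate an attrition rate of approximately 15-20% due to dropouts or failure to complete the required minimum of 85% of classes". Section G1 repeats that figure and adds that "we will recruit 40 subjects per group to account for attrition and data loss due to head motion", which makes 120 in total.

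Other safety sections also bear on this:

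- 8.b has the effects of medication withdrawal monitored through patient report, and says that "if the effects are too severe, participation in the study will be terminated prior to the second day of" off-medication testing.
- 8.e requires adverse events to go to the IRB at once and to prompt a review.
- 8.g covers events that are reported to the investigators after the study has ended.

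**The concern.** Someone who stops early has a last session too: the last one attended. For the 12 weeks after it, 8.f calls for adverse events to be documented, and 2.g, read as written, says nothing further is done. Staff handling a withdrawal are likely to turn to 2.g, because it is the section headed for that situation.

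People who leave are not a random subset as far as harm is concerned. Section 8.b itself foresees participation ending because of an ill effect, and the listed risks in 2.d include stumbling, mechanical injury and fatigue. If contact stops when such a person leaves, three things can go unrecorded: an event that appears later, the further course of an event already known, and a harm the person never mentioned before ceasing to attend. The twice-yearly assessment of risk against benefit (G2, H5, I1) would then draw on a safety record with a gap among the people in whom harm is a plausible reason for leaving.

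**Working it through.** **Step 1. The two rules side by side, for a participant who withdraws after session s.**

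| | 2.g | 8.f |
|---|---|---|
| Who | withdrawn participants | patients, no exception |
| Period | from withdrawal onward | 12 weeks from session s |
| Instruction | no follow-up | follow, and document adverse events |

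The periods overlap for the whole 12 weeks if withdrawal coincides with the last session. Nothing elsewhere ranks one rule above the other. G4 deals with dropouts, but only for outcome and imaging data.

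**Step 2. Do other sections fill the gap?** 8.e acts on events the team knows about. 8.g depends on the participant coming forward, and only after the study concludes. Neither requires anyone to contact a withdrawn participant. 2.f asks for no reason for leaving and no safety contact on exit.

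**Step 3. How many people?** Inputs: 120 randomized, 40 per group (G1); attrition 15-20% (2.e, G1).

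- 15%: 120 × 0.15 = 18 (40 × 0.15 = 6 per group if even)
- 20%: 120 × 0.20 = 24 (40 × 0.20 = 8 per group if even)

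These are upper bounds for 2.g. The attrition figure pools dropouts with people under 85% attendance. With 3 × 12 = 36 classes, 0.85 × 36 = 30.6, so 31 must be attended and a sixth absence falls short. Someone can miss six classes and remain in the study. The documents give no split between the two kinds of attrition.

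**Step 4. How much observation time?** Uncovered person-weeks = number withdrawn × 12.

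- 18 × 12 = 216
- 24 × 12 = 288

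As a share of what 8.f would cover if applied to everyone, assume that completers are observed for 24 weeks (12 of classes plus 12 after) and that every withdrawal happens at week w:

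share = (12 × n) / [(120 − n) × 24 + n × (w + 12)]

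| Attrition | w = 0 | w = 12 |
|---|---|---|
| 15% (n = 18) | 216 / 2,664 = 8.1% | 216 / 2,880 = 7.5% |
| 20% (n = 24) | 288 / 2,592 = 11.1% | 288 / 2,880 = 10.0% |

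The share changes little with the timing of withdrawal. The documents give no adverse event rate, so the number of missed events cannot be calculated.

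**The case against.** **2.g may mean evaluation visits only.** The protocol regularly uses the term follow-up for the third evaluation (E1, 2.c, F2, F7, G3). On that reading a site could cancel the remaining evaluations under 2.g and still document events under 8.f. This is a fair reading, so the two sections are not impossible to obey together. But 2.g's heading covers data collection generally, its sentence has no such limit, and nothing tells a site which reading applies. If the narrow meaning was intended, one sentence would settle it.

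**Known events are not lost.** This stands. Nothing in 2.g discards events already recorded, and 8.e covers any event the team knows of. A fall in a supervised class would normally be known before the person stops coming. Participants are also told how to reach the investigator about concerns outside sessions. A reader might infer that people who stop because of harm vanish from the safety record; the documents do not support that. What is exposed is active follow-up after exit, and harm not reported before it.

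**Low attendance is not withdrawal.** This also stands. A reader might infer from 2.e's heading that missing six classes puts a participant under 2.g. No section says so, and 2.f treats withdrawal as the participant's own act. The heading creates an ambiguity worth closing, nothing more.

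**Bias between arms.** A reader might infer that adverse event comparisons would be distorted by arm. G3 plans no such comparison, and the documents give neither event rates nor reasons for withdrawal by group. The claim cannot be supported.

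**Conclusion.** The inconsistency is real and unreconciled. As written, 2.g removes the 12-week adverse event period that 8.f sets, for anyone who withdraws. At most about 18 to 24 of 120 participants are affected, or 216 to 288 person-weeks. That is roughly 8% of planned adverse event observation at 15% attrition and 10-11% at 20%.

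These sizes assume that all expected attrition is withdrawal, which overstates the number; that each withdrawn participant would otherwise have the full 12 weeks; and that completers are observed for 24 weeks. The consequence is that delayed, evolving or unreported harms may be missed in people who leave. It does not extend to events the team already knew of, and no effect on a comparison between groups is shown. Nor does 8.f, even for completers, require open events to be followed to resolution, so that is not part of this point.

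The change is worth making because it is cheap and protects safety information where harm may be the reason for leaving.

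**What to change.** Reconcile 2.g with 8.f. Suggested wording for 2.g:

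> Withdrawal ends the remaining evaluation and MRI visits. Unless the participant also withdraws consent to be contacted, adverse events continue to be documented for the period in 8.f, counted as 12 weeks from the last session attended, for example by telephone.

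Add a cross-reference to 2.g in 8.f. In 2.e, state that attending fewer than 85% of classes is non-adherence and does not by itself end adverse event follow-up.

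The cost is a wording change and one or two short calls for each withdrawn participant: at the upper bound of 24 people, 24 to 48 calls over the whole study. The calls are a small new task for staff; no extra visit or assessment is needed.
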